[figure not shown]

## 2. LIST OF ABBREVIATIONS

[figure not shown]
Abbreviation	Definition
ACCP	Anti-Cyclic Citrullinated Peptide
ACR	American College of Rheumatology
AE	Adverse Event
anti-CCP	Anti-Citrullinated Protein Antibody
DAPSA	Disease Activity in Psoriatic Arthritis
DMARDs	Disease-Modifying Antirheumatic Drugs
EULAR	European League Against Rheumatism
GEP	Good Epidemiological Practice
GPP	Guidelines for Good Pharmacoepidemiology Practices
IEA	International Epidemiological Association
IEC	Independent Ethics Committee
IRB	Institutional Review Board
ISPE	International Society for Pharmacoepidemiology
ISPOR	International Society for Pharmacoeconomics and Outcomes Research
MTX	Methotrexate
NA	Not Applicable
PsA	Psoriatic Arthritis
RA	Rheumatoid Arthritis
SAP	Statistical Analysis Plan (if applicable)

PFIZER CONFIDENTIAL

Abbreviation	Definition
SPSS	Statistical Package for the Social Science (Software)
TNF	Tumor Necrosis Factor

PFIZER CONFIDENTIAL

[figure not shown]

#### **4. AMENDMENTS AND UPDATES**

Amendment number	Date	Protocol section(s) changed	Summary of amendment(s)	Reason
1	22 June 2021	Section 5	Updated to align with Study Report	Administrative
2	15 July 2021	8.6	Clarified tools used for data analysis	Administrative
3	26 July 2021	Throughout document	Spelling errors	Administrative
4	27 July 2021	Throughout document	Spelling errors	Administrative

[figure not shown]
**PFIZER CONFIDENTIAL**

## **5. MILESTONES**

Milestone	Planned date	Actual Date
Start of data collection	01 July 2020	01 July 2020
End of data collection	01 August 2020	01 August 2020
Final study report	30 June 2021	29 June 2021

**PFIZER CONFIDENTIAL**

## 6. RATIONALE AND BACKGROUND

Psoriatic arthritis is a chronic, systemic inflammatory arthritis that occurs in 6 to 42% of patients with psoriasis, affecting the peripheral joints, tendons, ligaments, and the axial skeleton. Current treatment guidelines for psoriatic arthritis recommends conventional synthetic disease-modifying antirheumatic drugs (DMARDs), such as methotrexate, as initial therapy, followed by biologic DMARDs (tumor necrosis factor [TNF] inhibitors, interleukin- 12 and interleukin-23 inhibitors, and interleukin-17 inhibitors) or apremilast in patients who had an inadequate response to conventional synthetic DMARDs.

The presence of anti-CCP antibodies in PsA and the prevalence was between 5.6 and 15.7% giving the optionality of biological treatment for RA patients, identifying a predictor for response will acquire more attention to rheumatologists for such patients.

Psoriatic arthritis is a severe form of arthritis in which deformities and joint damage develop in many patients. Bone erosions are observed in 47% of patients within the first 2 years, despite the use of traditional disease-modifying medications in more than half the patients. Furthermore, presence of ACCP in PsA patients consider one of bad prognostic factors for PsA Patients.

## 7. RESEARCH QUESTION AND OBJECTIVES

ACCP have been associated with lower response in PsA patients with positive ACCP. The objective is to evaluate the effect of ACCP on PsA patients and effect on their response to biological treatment.

## 8. RESEARCH METHODS

### 8.1. Study Design

- **Retrospective analysis** of patients with PsA that received etanercept from Baghdad Teaching Hospital (Rheumatology Center) from May 2012 until August 2019 (inclusion and exclusion criteria will apply for selecting patients).
- **Primary objective:** Determine the clinical impact of ACCP positivity for management (etanercept) in patients with PsA compared to negative ACCP patients.
- **Primary objective:** Determine the clinical impact of ACCP positivity for management (etanercept) in patients with PsA compared to negative ACCP patients.

## 8.2. Setting

### Patients and Methods

Data collected from the Baghdad Teaching Hospital registry. The rheumatology patient registry is a prospective longitudinal multicenter cohort initiated in 2012. It captures all patients treated with biologic therapies managed in the rheumatology department. The decision to initiate and maintain the treatment is guided by the American College of Rheumatology (ACR) recommendations.

### Study population

Patients will be included in the study if they meet the ACR/European League Against Rheumatism (EULAR) 2010 criteria for PsA with at least 1 year of follow-up after starting their first biologic therapy. This includes patients who were in monotherapy or in combination therapy with concomitant conventional DMARDs.

### Hypothesis

Our hypothesis is that there is no difference in response between sero-positive and sero-negative PsA patients to treatment with Enbrel.

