### 8.3. Data Sources

Patients with PsA will be identified in the rheumatology registry. Patient demographic information (age, gender), education level (years), present smoking status, disease duration (years), current MTX and steroid therapy (yes/no), baseline DAPSA (Disease Activity in Psoriatic Arthritis), anti-citrullinated protein antibody (ACCP) status will be obtained. Primary Outcomes: DAPSA in first and last follow up visit.

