#### **8.4. Study Size**

There is no pre-identified study size. All patients that meet the criteria will be entered into the study.

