#### **8.6. Data Analysis**

Categorical covariates will be described by frequency distribution while continuous covariates expressed in terms of their mean and standard deviation or median and interquartile range as appropriate. Patients will be divided for sero-positive PsA and sero-negative PsA (according to ACCP status) the unadjusted comparisons between groups of the covariates and the outcomes are evaluated using chi tests for categorical data, while for continuous data, we used the student's t-test for normally distributed variables and the Kruskall-Wallis test for non-parametric data.

We determined the effect of sero-positive on the biologic treatment response patients with PsA a multivariate analysis by using a stepwise linear regression model. The response variable is defined as disease activity index (either DAPSA, DAS-28 ESR, or DAS-28 CRP) at last visit. The baseline variables considered demographic data, disease duration (years), methotrexate (yes/no), current steroid therapy (yes/no), baseline disease activity index, anti-CCP (yes/no), psoriasis presentation and present smoking (yes/no).

We determined the effect of response by using change from baseline in disease activity index at the last visit. P value <0.05 is considered statistically significant, without multiplicity adjustment, for this post-hoc analysis.

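### Section 8.6 estimates the ACCP effect, the subject of the primary objective, by stepwise regression that is not said to retain ACCP, so the adjusted estimate may be missing or too large

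*Combined protocol and SAP*

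**What the plan says.** Section 8.1 gives the primary objective: "Determine the clinical impact of ACCP positivity for management (etanercept) in patients with PsA compared to negative ACCP patients". Section 7 is equally open about direction: "The objective is to evaluate the effect of ACCP on PsA patients and effect on their response to biological treatment". The Hypothesis paragraph in Section 8.2 reads "Our hypothesis is that there is no difference in response between sero-positive and sero-negative PsA patients to treatment with Enbrel".

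Section 8.6 plans two kinds of comparison. The first is a set of unadjusted tests of covariates and outcomes between ACCP groups. The second is "a multivariate analysis by using a stepwise linear regression model". Its candidates are demographic data, disease duration, methotrexate, steroids, baseline disease activity, anti-CCP, psoriasis presentation and smoking. The outcome is left open: "The response variable is defined as disease activity index (either DAPSA, DAS-28 ESR, or DAS-28 CRP) at last visit". Section 8.3 names one index: "Primary Outcomes: DAPSA in first and last follow up visit". The only decision rule is "P value <0.05 is considered statistically significant, without multiplicity adjustment, for this post-hoc analysis".

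The plan does not state that ACCP stays in the model, what the entry and removal thresholds are, or that a confidence interval will be given for the ACCP difference. Section 8.4 says "There is no pre-identified study size".

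**The concern.** Stepwise selection decides which candidates predict the outcome. The study asks a different question: how large the difference is for one named exposure after adjustment. That number is wanted whether it is large, small or near zero.

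Selection works against this in both directions. When the ACCP difference is small or imprecisely estimated, the term tends to drop out and the final model says nothing about its size or uncertainty. When the term stays in, it does so because the sample estimate was large enough to pass a significance filter. The retained estimate is then biased away from zero, and the usual P-value treats the model as if it had been fixed in advance.

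The adjusted comparison matters because the ACCP groups are not randomised and may differ in baseline activity, disease duration or concomitant treatment.

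**Working it through.** The plan states no sample size, SD, effect size or selection threshold, so it has no figure to reproduce. What follows is an illustration.

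**Inputs**
- ACCP prevalence 5.6% and 15.7%: background range in Section 6, assumed to apply here.
- Total N of 100 and 200: assumed.
- Entry P<0.05, removal P>0.10: assumed.
- Eight other independent candidates, one of them prognostic: assumed. Eight matches the Section 8.6 list if demographic data means age and gender.
- Residual SD of 1; true ACCP effect of 0 or 0.5 SD: assumed.

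**Step 1: no true effect.** With independent candidates, ACCP enters in roughly 5% of samples at an entry level of 0.05, so it should be absent in about 95%. Simulation (400 runs per setting) gave 93 to 96%, and a repeat gave about 94 to 97%. A larger sample does not change this: at N=400 the figures were 94.5% and 95.3%.

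**Step 2: true effect of 0.5 SD, chance that ACCP is absent.** SE = sqrt(1/n1 + 1/n0), where n1 and n0 are the numbers of ACCP positives and negatives. ACCP must exceed about c = 1.96 x SE to enter. The approximate chance of absence is one minus the power of the two-group test.

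| N | Positive v negative | SE | c | 1 - power | Simulated absence |
|---|---|---|---|---|---|
| 100 | 6 v 94 | 0.421 | 0.83 | 78% | 77% |
| 100 | 16 v 84 | 0.273 | 0.53 | 55% | 55% |
| 200 | 11 v 189 | 0.310 | 0.61 | 64% | 60% |
| 200 | 31 v 169 | 0.195 | 0.38 | 28% | 27% |

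**Step 3: size of the estimate when ACCP is kept.** In the first three rows c is above the true 0.5, so an estimate near the truth would usually be filtered out. For a normal estimate that must exceed c, the mean is 0.5 + SE x phi(z)/(1 - Phi(z)), with z = (c - 0.5)/SE.
- 6 v 94: z = 0.773; 0.5 + 0.421 x 0.296/0.220 = 1.07. Simulated 1.12.
- 16 v 84: z = 0.127; 0.5 + 0.273 x 0.396/0.450 = 0.74. Simulated 0.75.
- 11 v 189: z = 0.348; 0.5 + 0.310 x 0.376/0.364 = 0.82. Simulated 0.82.
- 31 v 169: z = -0.599; 0.5 + 0.195 x 0.333/0.725 = 0.59. Simulated 0.58.

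The repeat simulation gave 0.61 to 1.05 SD. The inflation shrinks as N grows: at N=400 the simulated means were 0.64 and 0.51 SD.

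**Step 4: last-visit score or change from baseline.** Let Y be the last-visit score, A ACCP status and B baseline. If Y = a + bA + gB, then Y - B = a + bA + (g - 1)B. The coefficient b is the same. So in a linear model containing baseline, with the same index and the same patients, the two outcomes give one ACCP difference. This does not carry over to the unadjusted comparisons, where they can differ.

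**The case against.** **The regression is meant to answer the ACCP question.** Section 8.6 gives the effect of seropositivity as its purpose and does not say that an unselected term goes unreported. That stands: one may say that the adjusted estimate may be missing, not that it will be. The written procedure still does not guarantee it.

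**ACCP is compared in any case.** The unadjusted comparisons of outcomes by ACCP group do not depend on selection. This also stands, and it limits the point to the adjusted result.

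**The 'no difference' hypothesis is just a null.** A reader might infer that the sponsor will take P>=0.05 as proof of no difference, or that it has already done so. The documents do not support either. The Hypothesis paragraph reads naturally as a formal null, Sections 7 and 8.1 ask an open question, and no passage claims equivalence or shows how the report worded its result. What remains is an omission: the plan does not say how P>=0.05 is to be read.

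**The study is finished and labelled post-hoc.** The post-hoc wording in Section 8.6 goes with its statement on multiplicity and does not justify letting the exposure leave the model. The 15 July 2021 change to Section 8.6 was administrative, so it is weak precedent for replacing the main model. Availability of the dataset is also not stated. These limit the weight of any correction, not the reason for making it.

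**Conclusion.** The point holds for the adjusted analysis. Followed literally, Section 8.6 does not secure an adjusted estimate of the effect named in the primary objective, and favours overestimates when it gives one. Under the stated assumptions, ACCP is absent from about 95% of final models when there is no true effect. A true 0.5 SD effect is absent in 27 to 77% of runs at N of 100 to 200 and averages about 0.6 to 1.1 SD when kept.

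These sizes depend on assumed thresholds, N, effect size and independent candidates. The direction of the problem does not depend on the exact values, although the inflation becomes small when ACCP positives are many. The real size cannot be computed, because neither N nor the number of ACCP positives is given. This is a gap in the plan, worth correcting; it is not evidence that the reported result is wrong.

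**What to change.** In Section 8.6, replace stepwise selection with a linear model for last-visit DAPSA, the index named in Section 8.3. The model should always contain ACCP status and baseline DAPSA, plus as many of the listed covariates as the number of patients and of ACCP positives can support. Report the adjusted ACCP difference with its 95% CI, and the number of ACCP positives.

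Add one sentence to the Hypothesis paragraph or Section 8.6: P>=0.05 alone does not support no difference, and the CI is to be read instead.

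Label all of this as decided after data collection (ended 1 August 2020) and after the 29 June 2021 report.

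The cost is one rerun, if the dataset is still available, a short amendment and possibly a report addendum. No new patients are needed. The result may prove inconclusive. With an assumed baseline correlation of 0.5 (residual SD sqrt(1 - 0.25) = 0.866), the adjusted 95% CI half-width would be 0.72 to 0.47 SD at N=100 and 0.33 to 0.21 SD at N=500, across the same prevalence range. An analysis chosen now also carries less weight than one fixed in advance.

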#### 8.2.1. Inclusion Criteria

Patients must meet all the following inclusion criteria to be eligible for inclusion in the study:

1. Diagnosed PsA patients.
2.  $\geq 18$  years of age.
3. Have not received previous biological treatment.

#### 8.2.2. Exclusion Criteria

Patients meeting any of the following criteria will not be included in the study:

1. Previous use of other biological treatments.
2. Etanercept use for less than 1-year duration.

### 8.3. Data Sources

Patients with PsA will be identified in the rheumatology registry. Patient demographic information (age, gender), education level (years), present smoking status, disease duration (years), current MTX and steroid therapy (yes/no), baseline DAPSA (Disease Activity in Psoriatic Arthritis), anti-citrullinated protein antibody (ACCP) status will be obtained. Primary Outcomes: DAPSA in first and last follow up visit.

#### **8.4. Study Size**

There is no pre-identified study size. All patients that meet the criteria will be entered into the study.

#### **8.5. Data Management**

The structured data is exported into an Excel spreadsheet and then transferred to the SPSS database (version 23) for statistical analysis.

#### **8.6. Data Analysis**

Categorical covariates will be described by frequency distribution while continuous covariates expressed in terms of their mean and standard deviation or median and interquartile range as appropriate. Patients will be divided for sero-positive PsA and sero-negative PsA (according to ACCP status) the unadjusted comparisons between groups of the covariates and the outcomes are evaluated using chi tests for categorical data, while for continuous data, we used the student's t-test for normally distributed variables and the Kruskall-Wallis test for non-parametric data.

We determined the effect of sero-positive on the biologic treatment response patients with PsA a multivariate analysis by using a stepwise linear regression model. The response variable is defined as disease activity index (either DAPSA, DAS-28 ESR, or DAS-28 CRP) at last visit. The baseline variables considered demographic data, disease duration (years), methotrexate (yes/no), current steroid therapy (yes/no), baseline disease activity index, anti-CCP (yes/no), psoriasis presentation and present smoking (yes/no).

We determined the effect of response by using change from baseline in disease activity index at the last visit. P value <0.05 is considered statistically significant, without multiplicity adjustment, for this post-hoc analysis.

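### The primary exposure, anti-CCP, is only a candidate in a stepwise model, so its adjusted effect is reported only if it passes its own significance test

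*Combined protocol and SAP*

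**What the plan says.** Section 8.1 sets one comparison as the primary objective: "Determine the clinical impact of ACCP positivity for management (etanercept) in patients with PsA compared to negative ACCP patients". The Hypothesis paragraph in Section 8.2 states that "there is no difference in response between sero-positive and sero-negative PsA patients to treatment with Enbrel", with no margin.

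Section 8.6 plans two routes to this contrast. First, "the unadjusted comparisons between groups of the covariates and the outcomes are evaluated" by simple tests. Second, the effect of seropositivity on response is determined by "a multivariate analysis by using a stepwise linear regression model", with the disease activity index at the last visit as the response. The variables considered include demographics, disease duration, methotrexate and steroid use, and also "baseline disease activity index, anti-CCP (yes/no), psoriasis presentation and present smoking (yes/no"). Anti-CCP therefore has the same status as smoking or steroid use.

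The plan states no entry or removal threshold, no forced-in term, no full-model analysis and no confidence interval. It gives a p<0.05 rule. On size, Section 8.4 says "There is no pre-identified study size". Section 6 says of anti-CCP antibodies in PsA that "the prevalence was between 5.6 and 15.7" per cent.

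**The concern.** Stepwise selection is a tool for choosing predictors. The question here is the size of one named effect. Under the plan, whether an adjusted answer exists depends on the p-value of that answer.

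This can mislead in two ways. If anti-CCP is not selected, the adjusted analysis gives no estimate and no interval. Because the stated hypothesis is no difference, a reader may take the absence as confirmation, without seeing which differences the data still allow. If anti-CCP is selected, it was kept because its estimate was large relative to its standard error. The reported coefficient is then too large on average when power is low, and the usual p-value and interval ignore the selection.

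The same applies to baseline disease activity, which is also only a candidate and may be absent from the model that estimates the anti-CCP effect.

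**Working it through.** The plan gives no N, power or effect size, so there is no figure of its own to reproduce.

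**Inputs from the documents:** prevalence 5.6% to 15.7% (Section 6, a literature figure and not the registry's own fraction); significance level 0.05 (Section 8.6).

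**Assumptions:** N = 100, 200, 400; true adjusted effect 0, 0.5 or 0.8 residual SD; entry 0.05, removal 0.10; two-sided tests.

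**Step 1: analytic check.** With n1 seropositive and n0 seronegative patients and SD 1:

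- SE = √(1/n1 + 1/n0), and λ = d/SE.
- Probability of significance: P = Φ(λ − 1.96) + Φ(−λ − 1.96).
- Mean estimate given significance, divided by the truth: 1 + [φ(1.96 − λ) − φ(1.96 + λ)] / (λP).

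For N=100 at 5.6% (6 against 94) and d=0.5: SE = √(1/6 + 1/94) = 0.421, λ = 1.187, P = 0.22, ratio = 1 + (0.296 − 0.003)/(1.187 × 0.221) = 2.12. The smallest estimate that can reach significance is 1.96 × 0.421 = 0.83 SD, already above the true 0.5.

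For N=400 at 15.7% (63 against 337) and d=0.5: SE = 0.137, λ = 3.643, P = 0.954, ratio = 1.03.

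**Step 2: simulation of the planned procedure.** 4000 datasets per scenario, with nine candidates: anti-CCP, baseline index, age, sex, disease duration, methotrexate, steroid, psoriasis presentation and smoking. The other eight are independent of anti-CCP. Forward-backward stepwise selection is compared with a model that enters all nine.

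| N, prevalence | Kept, effect 0 | Kept, effect 0.5 | Mean if kept (ratio to 0.5) | Coverage if kept, effect 0.5 | Fixed-model 95% CI half-width (SD) |
|---|---|---|---|---|---|
| 100, 5.6% | 5.0% | 20.5% | 1.119 (2.24) | 85.6% | 0.905 |
| 100, 15.7% | 5.2% | 39.9% | 0.771 (1.54) | 92.5% | 0.572 |
| 200, 5.6% | 5.0% | 32.4% | 0.837 (1.67) | 91.6% | 0.623 |
| 200, 15.7% | 5.0% | 69.2% | 0.599 (1.20) | 96.2% | 0.391 |
| 400, 5.6% | 5.2% | 60.9% | 0.635 (1.27) | 96.0% | 0.433 |
| 400, 15.7% | 5.1% | 95.2% | 0.518 (1.04) | 97.2% | 0.273 |

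At 0.5 SD the fixed model averages 0.491 to 0.511 with coverage 94.9% to 95.4%. At 0.8 SD the ratio when kept is 1.213/0.8 = 1.52 and 0.909/0.8 = 1.14 at N=100, and 1.03 and 1.00 at N=400.

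**Step 3: check of the half-widths.** With nine terms and an intercept, half-width ≈ t(0.975, N−10) / √{N p(1−p)[1 − 8/(N−1)]}. At N=100 and p=0.056: 1.987/√(5.286 × 0.919) = 0.90. At N=400 and p=0.157: 1.966/√(52.94 × 0.980) = 0.27. Both agree with the table.

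**Step 4: sensitivity.** With entry 0.15 and removal 0.20 (ten candidates, 400 runs), N=100, 5.6% and 0.5 SD, anti-CCP is kept in 37% of runs at 1.85 times the truth. The problem is smaller but remains. With each covariate shifted by 0.4 SD in seropositive patients (500 runs per cell), coverage when kept at 0.5 SD falls to between 76% and 94%, the ratio runs from 2.3 to 1.1, and retention at zero effect reaches about 9%. The fixed model stays unbiased.

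**The case against.** The strongest reply has four parts.

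- **Another contrast is always available.** Section 8.6 compares outcomes by ACCP group without adjustment, and also refers to change from baseline. With covariates independent of anti-CCP, an unadjusted comparison of change at a true 0.5 SD averages 0.49 to 0.51 with coverage 94% to 96%, and its intervals are only about 2% to 15% wider than the fixed model's. This is correct in that setting. However, the change-from-baseline sentence names no between-group model and no covariates. In a non-randomised registry comparison, covariates may well differ by serostatus, and the regression is the plan's only means of allowing for that.
- **The 95% figure restates the significance level.** This is true, and a fixed model would be non-significant about as often (at 0.5 SD it is significant in 19.9% to 95.4% of runs, close to the stepwise retention). The loss is not of power. A fixed model still reports its estimate and interval when non-significant; the stepwise model does not.
- **Low power is not established.** This stands. No N, SD or effect size is given, and the exaggeration nearly disappears at high power: about 1.12 times at 80% power and 1.06 at 90%. For 80% power at 0.5 SD, about 595 patients are needed at 5.6% prevalence, or 238 at 15.7%. Whether the registry reaches those numbers cannot be read from the documents.
- **The analysis is declared post hoc and the study is finished.** This limits what a re-run can claim. It does not make the selected estimate sound.

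**Conclusion.** The concern holds. As written, the only adjusted analysis of the primary contrast yields an estimate only if anti-CCP survives selection, and Section 8.6 mentions no interval.

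The first consequence does not depend on sample size: with entry at 0.05 and no true difference, about 95% of analyses give no adjusted estimate. Over the same scenarios a fixed model's interval would extend 0.27 to 0.91 SD either side, so non-selection is not evidence of no difference.

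The second depends on power. At 0.5 SD the average exaggeration is 2.2 times at N=100 with 5.6% seropositive and negligible at N=400 with 15.7%. Coverage when kept is clearly low mainly at N=100.

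The reading of the plan is firm. The sizes rest on assumed N, effect and thresholds, on the literature prevalence and, in the main simulation, on covariates unrelated to serostatus.

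**What to change.** In Section 8.6, replace the stepwise model with one fixed linear model: last-visit disease activity on anti-CCP, the baseline value of the same index, and the covariates already listed there (demographics, disease duration, methotrexate, steroid, psoriasis presentation, smoking), all entered. If seropositive patients are few, shorten the covariate list on stated subject-matter grounds and not by p-value, and always keep anti-CCP and the baseline index. Report the anti-CCP coefficient with its 95% CI whatever its p-value. Label any stepwise run exploratory, and state that non-selection is not evidence of no difference.

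One index must also be named, because Section 8.6 allows three and the single model could otherwise become three. Section 8.3 names DAPSA as the primary outcome.

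The cost is small. Section 5 shows data collection ended on 01 August 2020 and dates the "Final study report" 29 June 2021. The change is therefore a re-run on the existing SPSS data (ENTER in place of STEPWISE), a rewritten paragraph, an amendment entry and a report update. It uses a few more degrees of freedom. It remains post hoc and cannot be presented as pre-specified.

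### Section 8.3 makes DAPSA the only primary outcome, but Section 8.6 lets the response be DAPSA, DAS-28 ESR or DAS-28 CRP without saying which one decides

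*Combined protocol and SAP*

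**What the plan says.** Section 8.3 (Data Sources) names one outcome measure: "Primary Outcomes: DAPSA in first and last follow up visit". The only baseline index on its list of data items is also DAPSA: "baseline DAPSA (Disease Activity in Psoriatic Arthritis), anti-citrullinated protein antibody (ACCP) status will be obtained".

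Section 8.6 (Data Analysis) sets out a stepwise linear regression for the effect of seropositivity and defines its outcome more widely: "The response variable is defined as disease activity index (either DAPSA, DAS-28 ESR, or DAS-28 CRP) at last visit". The baseline covariate in that model is an unnamed disease activity index. The next paragraph brings in a second form of the response, again without naming an index: "We determined the effect of response by using change from baseline in disease activity index at the last visit". The section ends with the decision rule: "P value <0.05 is considered statistically significant, without multiplicity adjustment, for this post-hoc analysis".

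DAS-28 appears nowhere else in the documents supplied, including the abbreviation list. The research question (Section 7), the primary objective (Section 8.1) and the hypothesis (Section 8.2) name no index.

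**The concern.** The two sections do not agree on what the primary objective is judged by. One analyst could report DAPSA and another DAS-28 CRP, one as a last-visit value and the other as a change, and both would comply with Section 8.6. The results may differ, and a reader would have no basis in the plan for saying which was meant to decide.

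The risk runs both ways. An open choice can favour a significant ACCP effect, which would agree with the lower response in ACCP-positive patients asserted in Section 7. It can equally favour a non-significant result, which would agree with the stated hypothesis: "Our hypothesis is that there is no difference in response between sero-positive and sero-negative PsA patients to treatment with Enbrel". Section 8.4 sets no sample size, so no power calculation tied to a particular index shows what was intended.

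**Working it through.** **Setting the sections side by side**

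| Item | Section 8.3 | Section 8.6 |
|---|---|---|
| Index for the outcome | DAPSA only | DAPSA, DAS-28 ESR or DAS-28 CRP |
| Baseline index | DAPSA | index not named |
| Form of the response | first and last follow-up visit | last-visit value in the regression; change from baseline in the next paragraph |
| Ranking or selection rule | one outcome, so none needed | none |

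Section 8.6 does not refer back to Section 8.3, and no other section reconciles the two.

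**Illustrating the size**

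The plan states no figure to reproduce. Its only numerical input is P<0.05 per test without adjustment; I take this as two-sided, since sidedness is not stated. Everything else here is an assumption: three test statistics with equal pairwise correlation r, and all three indices treated as primary.

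*No true effect.* If the tests were independent, the chance of at least one P<0.05 would be 1 − 0.95³ = 0.143. For correlated tests, write each statistic as Z = √r·U + √(1−r)·e, with U shared and e separate. Given U = u, let

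q(u) = Φ((1.96 − √r·u)/√(1−r)) − Φ((−1.96 − √r·u)/√(1−r)).

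The chance of at least one P<0.05 is then 1 − ∫ q(u)³ φ(u) du.

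*A true effect with 80% power on each index.* Each statistic has mean 1.96 + 0.84 = 2.80. Subtract 2.80 inside both brackets of q(u). The chance that at least one index gives P≥0.05 is 1 − ∫ (1 − q(u))³ φ(u) du.

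| Assumed r | No effect: at least one P<0.05 | 80% power each: at least one P≥0.05 |
|---|---|---|
| 0.5 | 12.5% | 39% |
| 0.7 | 10.9% | 34% |
| 0.9 | 8.4% | 28% |
| 0.95 | 7.3% | 25% |
| one fixed index | 5% | 20% |

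*Three indices in two forms.* I simulated the null case with baseline-adjusted last-visit value and unadjusted change for each index. The assumptions were n = 200, 10% ACCP-positive (inside the 5.6% to 15.7% quoted in Section 6) and a baseline-to-last correlation of 0.3 to 0.7. The chance of at least one P<0.05 was roughly 10% when the indices correlate at 0.95, and 17% to 20% when they correlate at 0.5. The independent-test figure, 1 − 0.95⁶ = 0.265, overstates this because the two forms overlap heavily.

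**When the two forms coincide**

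Suppose last-visit value = a + b·ACCP + c·baseline + other terms. Subtracting baseline from both sides gives change = a + b·ACCP + (c − 1)·baseline + the same other terms. The ACCP coefficient b is the same, provided baseline stays in the model. In Section 8.6 baseline is only a candidate for stepwise selection and may drop out, so the two forms can differ as the plan stands.

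**The case against.** The best counter-argument is that Section 8.3 already settles the matter: it names DAPSA as primary, Section 8.6 never calls DAS-28 primary, and the wider wording may only mean that the same model is fitted to each available index and all are reported. That is a reasonable reading, and it makes this a conflict between two sections, not silence. But Section 8.6 does not say so, and it is the section that tests the ACCP effect.

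Second, the plan discloses that its p-values are post hoc and unadjusted. That stands, and no claim of overall 5% control is being broken. Disclosure does not tell the reader which index decides.

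Third, the missing DAS-28 entry in Section 8.3 is weak evidence on its own, because psoriasis presentation is also used in Section 8.6 and not listed there. I accept this: it leaves DAS-28 availability unknown and shows nothing about intent.

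Fourth, the magnitudes rest on assumed correlations, power and sample size, and selective choice is possible but not shown. Both are true. The contradiction does not depend on the figures.

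Last, the study is already reported, so a change may seem moot. It cannot restore prespecification, but readers still need to know which result answers the objective.

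**Conclusion.** The concern holds. Sections 8.3 and 8.6 conflict on the response variable, and Section 8.6 as written permits the deciding index, and its form, to be chosen after the data are seen.

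The effect on error rates is moderate. Under the working's assumptions, the false-positive chance rises from 5% to between about 7% and 13% over three indices, and to roughly 10% to 20% if both forms are tried as well. In the other direction, the chance of finding a non-significant index rises from 20% to between 25% and 39%. These ranges apply only if all three indices are treated as primary. The defect is an unfixed primary response that should be corrected; it is not a failure of promised error control.

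**What to change.** In Section 8.6:

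- Define the primary response as DAPSA at the last visit, adjusted for baseline DAPSA, in agreement with Section 8.3.
- Keep ACCP and baseline DAPSA in the model, outside the stepwise selection. Last-visit value and change then give the same ACCP coefficient, so one model covers both paragraphs.
- Label DAS-28 ESR and DAS-28 CRP models as supportive where those data exist, and add the indices to Section 8.3 if they are used. Do not mix indices across patients in one model.
- Report every index analysed with confidence intervals, and describe all p-values as nominal.

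The cost is a few sentences and, unless the reported model already has this form, a rerun of the DAPSA model. Patients without DAPSA leave the primary model.

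Timing limits what the change can claim. Section 5 dates the final report 29 June 2021. Section 4 lists the last amendment specific to Section 8.6 on 15 July 2021, followed by spelling edits throughout on 26 and 27 July. The revision should therefore be presented as a correction of labelling and reporting, not as prespecification.
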